### **SPYRAL HTN-OFF MED 80 PATIENT COHORT**

SPYRAL HTN-OFF MED is a multicenter, international, single-blind, randomized, sham-controlled trial. Eligible patients are drug-naive or discontinue their antihypertensive medications. Patients with an office systolic blood pressure (SBP) of 150 mm Hg or greater and less than 180 mm Hg, office diastolic blood pressure (DBP) of 90 mm Hg or greater, and a mean 24-h ambulatory SBP of 140 mm Hg or greater and less than 170 mm Hg at second screening, have renal angiography and are randomly assigned to renal denervation or sham control. Patients, caregivers, and those assessing blood pressure are blinded to randomization assignments.

While study enrollment is ongoing, data from the initial 80 patients with 3 months follow up from the SPYRAL HTN-OFF MED study was presented at ESC Congress in August 2017. Concurrently, an article presenting the data was published in the Lancet. A brief summary of the SPYRAL HTN-OFF MED data is provided below.

[figure not shown]
The primary endpoint, change in 24-h blood pressure at 3 months, was compared between groups. Drug surveillance was done to ensure patient compliance with absence of antihypertensive medication. The primary analysis was done in the intention-to-treat population. Safety events were assessed at 3 months.

Between June 25, 2015, and January 30, 2017, 353 patients were screened. 80 patients were randomly assigned to renal denervation (n=38) or sham control (n=42) and followed up for 3 months at 21 centers in the USA, Europe, Japan, and Australia.

There were no major adverse events in either group. No major procedural or clinical safety events were observed in either the renal denervation or sham control groups throughout the 3 months. Specifically, there were no deaths or occurrences of myocardial infarction, stroke, major bleeding, serum creatinine elevation greater than 50%, significant embolic events, vascular complications, renal artery re-intervention, new or worsening renal failure, or hypertensive emergency or crisis.

Office and 24-h ambulatory blood pressure decreased significantly from baseline to 3 months in the renal denervation group (Figure 3). No significant changes were seen in the sham-

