### F.7 Follow-Up Procedures

Subjects will return for in-office follow-up visits at week 2, 4 and 8 ( $\pm 3$  days) post-procedure. A phone call follow-up will be conducted at week 6 and 10 ( $\pm 3$  days) post-procedure. There will additionally be follow-up visits at 3 and 6 months ( $\pm 14$  days) post-procedure. Upon completion of the 3 month follow-up visit, a Medication Re-Introduction protocol to resume antihypertensive medications must be followed, if required. See instructions in Section F.9 for Medication Re-Introduction for Subjects with Systolic OBP  $\geq 140$  mmHg at 3M follow-up visit. Subjects will then return at 6 months ( $\pm 14$  days), 12, 24, and 36 months post-procedure with visits conducted  $\pm 30$  days, from the procedure date. In case of a crossover, subjects will return for in-office visits at 1, 3, 6, 12 and 24 months post-crossover procedure.

Alternative methods of data collection may be necessary in the case of extenuating circumstances, such as a global pandemic, when subjects are prohibited from coming into the office for required assessments. For all assessments completed via alternative methods in these circumstances, sites are not required to enter a protocol deviation for missing, and/or alternative data collection. Data unable to be collected remotely or via an alternative method should be collected at the next possible in-person visit. In the event a subject is unable to return for an in-office follow-up visit, the alternative methods of obtaining follow-up assessments are listed below:

- In-home visit by trained and delegated site personnel or designee, i.e. home health care personnel. The following assessments may not be completed with an in-home visit:
  - Renal Artery Imaging:
    - Make every effort to schedule in-person renal artery imaging as soon as possible.
    - When possible, the subjects may be referred to a local imaging center for assessment. Local imaging technicians would require study training and delegation prior to assessment.

In the event an in-home visit is not possible, the alternate methods for obtaining follow-up assessments are listed below:

- Virtual Visit, i.e. inclusive of video with study subject. The following assessments may not be completed with a virtual visit:
  - Clinical Assessment, limited review to be completed per physician discretion.
  - Laboratory Tests:

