- b) **SF-36:** The 36-Item Short Form Survey (SF-36) will be administered at the 3, 6, 12, 24 and 36 month post-procedure visits to measure health outcomes.
- c) **Clinical Assessment** will be conducted at all post-procedure follow-up visits to evaluate the subject's current medical condition. An individual experienced in performing histories and physical exams is required to assess subjects for safety assessment during the period of time that study subjects are not on antihypertensive medications.
- d) **Office Blood Pressure** measurements will be obtained in accordance with Appendix L.7 at all post-procedure follow-up visits.
- e) **Laboratory Tests:**
  - **Basic metabolic panel Chem-7 (blood):** serum-creatinine, sodium, potassium, blood urea nitrogen (BUN), bicarbonate, chloride and glucose. Bicarbonate will not be measured for subjects enrolled in Japan and Europe.
  - **eGFR** will be calculated from the serum-creatinine in the Chem-7 panel for eligibility criteria by using the 4 variable Modification of Diet in Renal Disease (MDRD) Formula or the local Japanese criteria for subjects enrolled in Japan.
  - **Renin and Aldosterone testing (blood; 3 month follow-up only)** Samples should be collected in the morning after the patient has been out of bed for  $\geq 2$  hours and after resting quietly after a minimum of 5 minutes but preferably 30 minutes. The time of day and subject's position (standing, sitting, or lying down) before the blood sample is collected should be documented and the same time of day ( $\pm 2$  hours) and subject position should be used for collection of blood samples for determination of renin and aldosterone at later time points in the study.
  - **Drug testing (urine/blood)** to ensure no medications are present in the subject's system at 3 months follow-up and to ensure that prescribed medications are in the subject's system at 6, 12, 24, and 36 months. A

urine sample will be collected, preferably using the subject's first morning urine. A blood sample will be collected at the time of the visit.

- f) **Initiate Medication Re-Introduction for Subjects with Systolic OBP  $\geq$  140 mmHg at 3M follow-up visit.** Starting at 3 month follow-up after clinical assessment and a valid ABPM are completed.
- g) **Medication & Adverse Event Reviews** will be completed at each follow-up visit to assess any changes in medication usage or medical condition:

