# 8. Determination of Sample Size

This study will be conducted as an adaptive Bayesian trial with an informative prior. A Bayesian power prior approach [3,4] in conjunction with a discount function will be used to incorporate the prior data. The discount function reduces the strength of the prior data if disagreements are observed with the pivotal data.

The prior data consists of the first consecutively randomized 80 patients in the SPYRAL HTN-OFF MED study, the results from these 80 subjects have been analyzed and published [6]. The weight of the prior data will be adjusted using a discount function, which scales from 0 to 1, according to the similarity of the prior and pivotal data. This discount function adjusts the amount of weight the prior receives. This prevents the use of an informative prior where exchangeability issues are present (e.g., the prior and pivotal data are quite different). This discount function approach was proposed by the Medical Device Innovative Consortium (MDIC) working group and is a collaborative effort between FDA and industry through the MDIC [1,2]. If the analyses show a high level of agreement for pivotal data compared to the prior, the prior will be weighted at or near 100%. If the pivotal data perform worse than or much better than the prior, then the prior will receive very little or zero weight. The Bayesian adaptive design is set up to enroll patients until a sufficient sample size is achieved to have high probability of meeting the endpoint.

The sample size of the study will vary from 210 to 300 subjects with 3-month follow-up due to the adaptive nature of the trial. This will require approximately 247 to 353 randomized subjects to account for a 15% attrition at 3-months. Based on this attrition rate, the interim analyses will take place after the 210th and 240th subjects have completed 3-month follow-up, with a maximum study size of 300 subjects if the study does not stop at either interim look. The actual rate of attrition will dictate the available sample size for analyses. At each interim analysis, enrollment may be stopped for efficacy or futility.

Simulations of trial design operating characteristics performed to demonstrate control of type I error & power are presented in section 9.9.6 for the primary and secondary efficacy endpoints.

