## 9.4. Handling of Missing Data and Dropouts

Every effort will be made to minimize missing data for the primary and secondary powered efficacy endpoints. A secondary analysis will be performed for both efficacy endpoints where missing outcome data are imputed using SAS PROC MI. Missing 3-month outcomes will be imputed using baseline SBP, treatment group, age, gender and BMI. One hundred imputed datasets will be generated, and a pooled estimate of the treatment effect will be generated using SAS PROC MIANALYZE.

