**Table 3: Simulation Assumptions for Primary Efficacy Endpoint** 

Enrollment Rate	10 Subjects / Month
Prior Baseline Adjusted RDN Group Mean/SE	-5.30 / 1.65 mmHg
Prior RDN Group N	35
Prior Baseline Adjusted Control Group Mean/SE	-0.74 / 1.62 mmHg
Prior Control Group N	36
Maximum Prior Patients	35 RDN + 36 Control = 71
Pivotal Study Expected Treatment Difference	-4.0 mmHg
Pivotal Study RDN Group Mean/SD	-4.74 / 12 mmHg
Pivotal Study Control Group Mean/SD	-0.74 / 12 mmHg

Weibull Discount Function Parameters	Shape: $k = 3$ , Scale: $\lambda = 0.5$
WCDUII DISCOULL LUICUOLLI UI ALAITICUCIS	$  J   apc. \kappa - J, J   apc. \kappa - 0.5$

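### The multiple imputation in SAP 9.4 uses no post-procedure readings, so it largely repeats the complete-case assumption and leaves collected off-medication office SBP unused

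*SAP*

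**What the plan says.** SAP 9.4 sets out one treatment of missing outcomes: "A secondary analysis will be performed for both efficacy endpoints where missing outcome data are imputed using SAS PROC MI". The predictors are fixed in the next sentence: "Missing 3-month outcomes will be imputed using baseline SBP, treatment group, age, gender and BMI". One hundred imputed datasets are pooled with PROC MIANALYZE. No other SAP section adds a post-baseline predictor, and 9.4 does not say whether the baseline SBP meant is ambulatory, office or both.

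Protocol F.7 provides post-baseline readings that could be used: "Subjects will return for in-office follow-up visits at week 2, 4 and 8", and office blood pressure "measurements will be obtained in accordance with Appendix L.7 at all post-procedure follow-up visits", which includes the 3-month visit. Weeks 6 and 10 are telephone contacts ("A phone call follow-up will be conducted at week 6 and 10"), so no office reading is routine then. ABPM is scheduled only at Screening Visit 2 and from 3 months on (Protocol Tables 1 and 4).

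The expected loss is not small. SAP section 8 states: "This will require approximately 247 to 353 randomized subjects to account for a 15% attrition at 3-months". In the ITT set, subjects who meet the escape criteria are carried forward by LOCF to 3 months (SAP 9.1.3.1).

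**The concern.** Apart from the predictive imputation used for futility, 9.4 is the only place where the SAP fills in missing 3-month outcomes for subjects who did not escape. The primary analysis otherwise rests on subjects with a 3-month value. An imputation is useful beside it only if it brings in information that the primary model lacks.

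The primary model already conditions on arm and baseline blood pressure. The imputation adds age, gender and BMI. It thus still assumes that a subject with missing data would have followed others with the same arm and baseline profile, whatever that subject's readings at weeks 2, 4 and 8 showed. If loss of the ABPM outcome is related to those readings, the complete-case and imputed estimates will share the same bias, and their agreement would be mistaken for reassurance.

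**Working it through.** **Inputs.** Randomised prior cohort: 38 denervation + 42 control = 80 (Protocol B.1.2). Prior N for ABPM: "35 RDN + 36 Control = 71" (SAP Table 3). Prior N for office SBP: 37 + 41 = 78 (SAP Table 4). Planning values: difference -4.0 with SD 12 for 24-hour SBP, and -6.5 with SD 16 for office SBP. Attrition: 15%. The documents give no correlation between office and ambulatory change, so r = 0.3 to 0.7 is assumed.

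**The plan's own figures.** n/(1 - 0.15): 210/0.85 = 247.1, 240/0.85 = 282.4, 300/0.85 = 352.9. These agree with the stated 247, 282 and 353.

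**How many subjects without ABPM had an office outcome (prior cohort).**

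| | Randomised | No ABPM outcome | No office outcome | At least this many without ABPM had office |
|---|---|---|---|---|
| RDN | 38 | 38 - 35 = 3 (7.9%) | 38 - 37 = 1 | 3 - 1 = 2 of 3 |
| Control | 42 | 42 - 36 = 6 (14.3%) | 42 - 41 = 1 | 6 - 1 = 5 of 6 |
| Total | 80 | 9 (11.25%) | 2 | 7 of 9 (78%) |

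**Gain in precision.** For a monotone bivariate-normal pattern, the variance ratio is 1 - r² × (n_aux - n_obs)/n_aux. Here n_obs is the fraction with ABPM and n_aux the fraction with ABPM or office SBP.
- At 15% missing with 7/9 having office SBP: n_obs = 0.85, n_aux = 0.85 + 0.15 × 7/9 = 0.967, and (n_aux - n_obs)/n_aux = 0.121. For r = 0.3, √(1 - 0.09 × 0.121) = 0.995. For r = 0.7, √(1 - 0.49 × 0.121) = 0.970. The SE falls by 0.5% to 3.0%.
- At 11.25% missing: n_obs = 0.8875, n_aux = 0.975, ratio 0.090. The SE falls by 0.4% to 2.2%.

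**Effect on the estimate.** A simulation used N = 353, a true difference of -4.0, SDs 12 and 16, 600 runs per scenario and 20 imputations. In the first scenario the ABPM outcome was more likely to be missing when office change was higher (about 13% missing).

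| r | Complete-case ANCOVA | Imputation from arm and baseline | Imputation with office SBP added | Shift from adding office SBP |
|---|---|---|---|---|
| 0.3 | -3.81 | -3.81 | -3.94 | -0.13 |
| 0.5 | -3.74 | -3.75 | -3.93 | -0.18 |
| 0.7 | -3.76 | -3.75 | -4.04 | -0.29 |

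When data were missing completely at random (15%), the three methods agreed to within 0.01: -3.97/-3.97/-3.97, -4.01/-4.00/-4.01 and -4.13/-4.13/-4.12 for the three values of r.

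**Limits of the simulation.** Each mean carries Monte Carlo error of about 0.05 to 0.06 (run-to-run SD 1.30 to 1.42, divided by √600). The comparison between methods on the same data is the part to read. Age, gender and BMI were not simulated, and baseline SBP was given no effect on the change. One office value was assumed present for every subject, which favours the revised model. The complete-case comparator is a plain ANCOVA without the prior.

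**The case against.** The case for leaving 9.4 alone has real substance.

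- **Escape subjects are handled elsewhere.** A reader might infer that subjects who leave because blood pressure rises off medication are imputed as average. The documents do not support that for anyone who meets the escape criteria: SAP 9.1.3.1 carries them forward, and 9.4 does not override it. What remains is subjects who withdraw or miss the ABPM without being classed as escapes. The documents do not count them. This objection stands.
- **The 7 of 9 is soft evidence.** It comes from nine prior-cohort subjects at one time point. The Ns of 71 and 78 may include LOCF values. Escape subjects have scheduled office readings but no scheduled ABPM (Protocol Tables 3 and 6), so some of the 7 may be escapes, whose 3-month office reading may be on medication. No pivotal counts are given, and no counts of completed week 2, 4 and 8 readings. This stands as a limit on how far the figure can be extended.
- **The predictive value of office SBP is assumed.** A reader might call these readings the strongest predictors of ambulatory change or of dropout. The documents contain no correlation and no dropout analysis to show that.
- **The revised model is still missing-at-random.** It cannot test missingness that depends on the unseen ABPM value itself. That is correct.
- **The analysis decides nothing.** Success turns on the posterior probability in SAP 9.8 and 9.9.3. Protocol B.1.2 already reports the 3-month result as -3.9 mmHg (95% BCI -6.2 to -1.6), with posterior probability above 0.999. That also stands, and it makes any change now post hoc.

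None of this answers the central point. The listed predictors make the secondary analysis almost a copy of the complete-case one, while relevant scheduled data go unused.

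**Conclusion.** The point holds as a modest weakness in a secondary analysis. The omission is plain in 9.4. In the simulation, imputation from arm and baseline returned the complete-case estimate to within about 0.01 mmHg, so it is hardly a separate sensitivity analysis. Adding off-medication office SBP would lower the SE by at most about 3%. It would move the estimate by about 0.1 to 0.3 mmHg if missingness depends on office SBP, and by almost nothing if data are missing completely at random. These sizes rest on the assumed r of 0.3 to 0.7, on the prior cohort's pattern of missing data, and on the simulated mechanism.

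A reader might go further and infer that the planned imputation hides a bias large enough to threaten the efficacy conclusion. The documents do not support that. The shift is small against -4.0, the imputation does not enter the success rule, and in the scenario simulated the baseline-only estimate lay nearer to zero than the truth. That direction belongs to the assumed mechanism and should not be generalised.

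**What to change.** Revise the PROC MI model in SAP 9.4, with separate predictor lists for the two endpoints.

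- **24-hour ABPM endpoint:** keep the listed variables and add off-medication office SBP at baseline, weeks 2, 4 and 8, and 3 months.
- **Office SBP endpoint:** keep the listed variables and add off-medication office SBP at weeks 2, 4 and 8, and the 3-month ABPM value where available. Do not add 3-month office SBP, which is the outcome.
- **Both endpoints:** keep the LOCF rule for escape subjects, exclude readings taken on antihypertensive medication, and state which baseline SBP is meant. Report how many subjects lack each outcome, by arm, and how many of them have each office reading.
- **Status:** label the revised imputation supplementary and justify it in the final study report, as the opening of Protocol section H provides, because 3-month results are already reported. State that it remains a missing-at-random analysis.

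Imputing separately by arm, and rerunning the Bayesian model on the imputed sets, are optional extras. The latter would need a pooling rule. Neither corrects a defect shown here.

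The cost is a few extra variables in existing code and a flag for off-medication readings. No new data are needed.

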# 9.5. Adjustments for Multiple Comparisons

The primary safety and efficacy endpoints are independently powered and no adjustments for multiple comparisons will be made.

## 9.6. Demographic and Other Baseline Characteristics

Baseline variables will be tabulated. Categorical variables, including binary variables, will be reported by giving the number and percentage of patients in each category. Continuous variables will be reported by presenting the number of values, mean, standard deviation, median, minimum, and maximum value for each. No imputation will be performed for missing data unless otherwise stated.

#### 9.7. Treatment Characteristics

Renal denervation treatment measures such as number of ablation attempts and number of generator codes will be summarized separately for each kidney, and for combined kidneys. Anti-hypertensive medication use will also be summarized at baseline and at each follow-up.

## 9.8. Interim Analyses

Interim analyses will be conducted and reviewed by the DSMB, along with an independent organization that will be performing the Bayesian analyses. Medtronic personnel will not have access to any unblinded results prior to the primary endpoint analyses. The interim analyses will take place at N=210 and N=240 subjects with 3-month follow-up, with a maximum study size of N=300 subjects if the study does not stop at either interim look. At each interim analysis, enrollment may be stopped for efficacy or expected futility. Both the primary and secondary effectiveness endpoints will be evaluated during these interim looks and enrollment will only stop at an interim analysis if both endpoints meet the following stopping criteria.

- 1. The first interim analysis takes place when the first 210 subjects have 3-month follow-up data available (requiring approximately 247 randomized subjects to account for attrition). The Bayesian efficacy analysis will be performed and P[suc] will be calculated, where P[suc] is the probability of accepting the alternative efficacy endpoint hypotheses,  $P(\mu < 0 | y, y_0, \widehat{\alpha_0}(y, y_0, \lambda, k))$ , and is defined in detail in section 9.9.3.
  - a. If P[suc] > 0.975 for both the primary and secondary efficacy endpoints, then the study has met the efficacy hypotheses and enrollment will be stopped. Any additional subjects that have been enrolled before the decision is made to stop for efficacy will be pooled with the existing subjects and analyzed as a secondary cohort.
  - b. We calculate the probability of futility based on the maximum study size of 300 subjects which requires us to impute the outcomes for subjects who have not yet been enrolled (see sections 9.8.2 and 9.8.3 below for details). If the posterior probability of futility from this calculation is < 0.05 for both the primary and secondary efficacy endpoints, then the study will have met the futility boundary and enrollment will be stopped. Any additional subjects that have been enrolled before the decision is made to stop for futility will be pooled with the existing subjects and analyzed as a secondary cohort.

  - c. If the stopping rules in a and b above are not met for either the primary or secondary efficacy endpoints, then we continue enrolling subjects to the second interim analysis.
- 2. If we don't stop for efficacy or futility at the first interim analysis then enrollment will continue until the second interim analysis when 3-month follow-up data is available for the first 240 subjects (requiring approximately 282 randomized subjects to account for attrition). The Bayesian efficacy analysis will be performed and P[suc] will be calculated.
  - a. If P[suc] > 0.975 for both the primary and secondary efficacy endpoints, then the study has met the efficacy hypotheses and enrollment will be stopped. Any additional subjects that have been enrolled before the decision is made to stop for efficacy will be pooled with the existing subjects and analyzed as a secondary cohort.
  - b. We calculate the probability of futility based on the maximum study size of 300 subjects which requires us to impute the outcomes for subjects who have not yet been enrolled (see sections 9.8.2 and 9.8.3 below for details). If the posterior probability of futility from this calculation is < 0.05 for both the primary and secondary efficacy endpoints, then the study will have met the futility boundary and enrollment will be stopped. Any additional

- subjects that have been enrolled before the decision is made to stop for futility will be pooled with the existing subjects and analyzed as a secondary cohort.
- c. If the stopping rules in a and b above are not met for either the primary or secondary efficacy endpoints, then we continue enrolling subjects to the final analysis.
- 3. If we don't stop for efficacy or futility at the second interim analysis, then enrollment will continue until the maximum study size of 300 subjects with 3-month follow-up data (requiring approximately 353 randomized subjects to account for attrition). The Bayesian efficacy analysis will be performed and P[suc] will be calculated.
  - a. If P[suc] > 0.975 for the primary efficacy endpoint, then we have met the primary efficacy hypothesis.
  - b. If P[suc] > 0.975 for the secondary efficacy endpoint, then we have met the secondary efficacy hypothesis.

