organization that will be performing the Bayesian analyses. Medtronic personnel will not have access to any unblinded results prior to the primary endpoint analyses. At each interim analysis, enrollment may be stopped for futility or efficacy. Both the primary and secondary effectiveness endpoints will be evaluated during these interim looks and enrollment will only stop at an interim analysis if both endpoints meet the following stopping criteria.

1. The first interim analysis takes place when the first 210 subjects have 3-month follow-up data available (requiring approximately 247 randomized subjects to account for attrition). The Bayesian efficacy analysis will be performed and  $P[\text{suc}]$  will be calculated, where  $P[\text{suc}]$  is the probability of accepting the alternative efficacy endpoint hypotheses,  $P(\mu < 0 | y, y_0, \hat{\alpha}_0(y, y_0, \lambda, k))$ , , and is defined in detail in section H4.
  - a. If  $P[\text{suc}] > 0.975$  for both the primary and secondary efficacy endpoints, then the study has met the efficacy hypotheses and enrollment will be stopped. Any additional subjects that have been enrolled before the decision is made to stop for efficacy will be pooled with the existing subjects and analyzed as a secondary cohort.
  - b. We calculate the probability of futility based on the maximum study size of 300 evaluable subjects which requires us to impute the outcomes for subjects who have not yet been enrolled. If the posterior probability of futility from this calculation is  $< 0.05$  for both the primary and secondary efficacy endpoints, then the study will have met the futility boundary and enrollment will be stopped.. Further details can be found in the study SAP. Any additional subjects that have been enrolled before the decision is made to stop for futility will be pooled with the existing subjects and analyzed as a secondary cohort.
  - c. If  $P[\text{suc}]$  is  $\geq 0.05$  and  $\leq 0.975$  for either the primary or secondary efficacy endpoints, then subject enrollment will continue to the second interim analysis.
2. If the study doesn't stop for efficacy or futility at the first interim analysis then enrollment will continue until the second interim analysis when 3-month follow-up data is available for the first 240 subjects (requiring approximately 282 randomized subjects to account for attrition). The Bayesian efficacy analysis will be performed and  $P[\text{suc}]$  will be calculated.

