  - a. If  $P[\text{suc}] > 0.975$  for both the primary and secondary efficacy endpoints, then the study has met the efficacy hypotheses and enrollment will be stopped. Any additional subjects that have been enrolled before the decision is made to stop for efficacy will be pooled with the existing subjects and analyzed as a secondary cohort.
  - b. We calculate the probability of futility based on the maximum study size of 300 evaluable subjects which requires us to impute the outcomes for subjects who have not yet been enrolled. If the posterior probability of futility from this calculation is  $< 0.05$  for both the primary and secondary efficacy endpoints, then the study will have met the futility boundary and enrollment will be stopped. Further details can be found in the study SAP. Any additional subjects that have been enrolled before the decision is made to stop for futility will be pooled with the existing subjects and analyzed as a secondary cohort.
  - c. If  $P[\text{suc}]$  is  $\geq 0.05$  and  $\leq 0.975$  for either the primary or secondary efficacy endpoints, then we continue enrolling subjects to the final analysis.

3. If the study doesn't stop for efficacy or futility at the second interim analysis then enrollment will continue until the maximum study size of 300 subjects with 3-month follow-up data (requiring approximately 353 randomized subjects to account for attrition). The Bayesian efficacy analysis will be performed and  $P[\text{suc}]$  will be calculated.
  - a. If  $P[\text{suc}] > 0.975$  for the primary efficacy endpoint, then we have met the primary efficacy hypothesis.
  - b. If  $P[\text{suc}] > 0.975$  for the secondary efficacy endpoint, then we have met the secondary efficacy hypothesis.

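### Does the futility rule name the wrong quantity, and does it clash with the protocol's continuation rule?

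*SAP*

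**What the plan says.** At each interim look both documents give three rules, applied to 24-hour and office systolic pressure.

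- **Rule a, efficacy.** Stop if P[suc] exceeds 0.975 on both endpoints. Protocol C.6 says that P[suc] "is the probability of accepting the alternative efficacy endpoint hypotheses" and then writes it as the posterior probability that μ is below zero, given the data in hand and the discounted prior.
- **Rule b, futility.** SAP 9.8 stops enrolment "If the posterior probability of futility from this calculation is < 0.05 for both the primary and secondary efficacy endpoints", and in the same item sends the reader to 9.8.2 and 9.8.3. Protocol items 1b and 2b open identically ("If the posterior probability of futility from this calculation is", then the 0.05 limit), say that enrolment is stopped, and refer to the SAP for details.
- **Rule c, continuation.** In the protocol, a P[suc] from 0.05 to 0.975 "for either the primary or secondary efficacy endpoints, then subject enrollment will continue to the second interim analysis"; item 2c does the same at the second look ("for either the primary or secondary efficacy endpoints, then we continue enrolling subjects to the final analysis"). SAP 1c and 2c have no band: "If the stopping rules in a and b above are not met for either the primary or secondary efficacy endpoints", enrolment goes on.

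SAP 9.8.2 defines the futility quantity as the share of completed datasets in which the success criterion is met, with a stop below 0.05. SAP 9.8.3 says the same in words and describes how outcomes are imputed up to 300 subjects using the prior data.

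**The concern.** There are two separate difficulties.

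First, rule b compares a probability of futility with 0.05 and stops when it is small. As worded, that is the wrong way round.

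Second, once rule b is read as SAP 9.8.2 intends, it concerns predictive success at 300 subjects, while protocol rule c concerns the current posterior. The same figure, 0.05, is applied to different quantities. On the same data, protocol rule b can say stop while protocol rule c says continue.

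A stopping rule should give one instruction. Had the pivotal data shown no effect, the choice of rule would have decided whether enrolment ran on from 210 to as many as 300 evaluable subjects. By the plan's own figures that is 353 − 247 = 106 further randomized subjects in a trial with little chance of success.

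**Working it through.** **Inputs.** Looks at n = 210 and 240 with a maximum N = 300; efficacy threshold 0.975, so z = 1.96; futility threshold 0.05, so z = 1.645 (SAP 9.8 to 9.8.3). Prior means, standard errors, SDs of 12 and 16 mmHg and the Weibull parameters come from SAP Tables 3 and 4. The correlation between the endpoints is not given and is assumed where needed.

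**The plan's own figure.** SAP Table 5 and protocol Table 13 report futility stops in 0.05% of simulations under the design effects, which is 4 of 8,000. A simplified simulation with rule b read as predictive success gives 0.06%, 0.08% and 0.41% at correlations of 0, 0.4 and 0.7. Both other readings (literal rule b after rule a, or P[suc] below 0.05 on both endpoints) give 0.0%. The published figure fits the intended rule at low correlation, but every reading lies so close to zero that it discriminates only weakly.

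**Where intended rule b fires, without borrowing.** Let t = n/N and P[suc] = Φ(z). Predictive success is

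PP = Φ[(z − 1.96√t) / √(1 − t)].

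PP < 0.05 requires z < 1.96√t − 1.645√(1 − t).

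- n = 210, t = 0.7: z < 1.640 − 0.901 = 0.739, so P[suc] < 0.770.
- n = 240, t = 0.8: z < 1.753 − 0.736 = 1.017, so P[suc] < 0.846.

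At P[suc] = 0.50 and n = 210, z = 0 and PP = Φ(−1.640/0.5477) = Φ(−2.994) = 0.0014. Rule b says stop while protocol rule c says continue. The two collide whenever both endpoints lie below the cut-off and at least one is at 0.05 or above. With borrowing and the control arm at its prior mean, the cut-offs move little: 0.77 to 0.79 at 210 and 0.84 to 0.85 at 240.

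**Where literal rule b fires.** A futility probability 1 − PP < 0.05 requires z > 1.96√t + 1.645√(1 − t).

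- n = 210: z > 1.640 + 0.901 = 2.541, so P[suc] > 0.9945.
- n = 240: z > 1.753 + 0.736 = 2.489, so P[suc] > 0.9936.

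Both exceed 0.975, so rule a is already met. With borrowing, none of 64,000 simulated trials (no effect and design effects, several correlations) met literal rule b without rule a.

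**The passages together.** SAP 1b and 2b name their own formula, and SAP 1c and 2c refer back to rules a and b, so the SAP gives one instruction. In the protocol, item 2 takes up the study that does not "stop for efficacy or futility at the first interim analysis then enrollment will continue", and item 3 the study that does not "stop for efficacy or futility at the second interim analysis then enrollment will continue until the maximum study size of 300 subjects". Both treat continuation as the remainder after rules a and b. The protocol gives no futility formula that competes with the SAP's.

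**What happened.** Protocol B.1.2 reports that enrolment stopped for efficacy after the first interim analysis in February 2020, with posterior probabilities above 0.999 on both endpoints. That is far from any futility region.

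**The case for a change.** The best case for a change is that the overlap is wide, the wording still stands in the current versions, and the repair is a few words. With no true effect and an assumed correlation of 0.4, the SAP rule stops about 76% of trials for futility. Stopping only when P[suc] is below 0.05 on both endpoints, which is close to what the protocol band implies, stops about 1.1%. As written, these would be very different rules.

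The overlap stands, and so does the mislabelling. Three things weaken the rest.

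- It goes too far to say that the protocol leaves open which rule governs. Rule b is a direct instruction to stop, items 2 and 3 make continuation conditional on no stop, and the SAP says so outright. The verbal definition of P[suc] also comes close to how SAP 9.8.3 describes the predictive quantity, so the lower limit of the band looks like a mirror of rule b written with the wrong symbol.
- The requirement in protocol section H to report deviations covers that section and the SAP. The conflict lies in C.6, and no futility decision was taken.
- The simulated shares rest on an assumed correlation and a simplified model, which gives 78% to 81% first-look power for both endpoints against the stated 83%. They show direction only; the closed-form cut-offs carry the point.

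A new wording would also need care. The formula in SAP 9.8.2 does not show the prior data, which enter in 9.8.3, so the two have to be read together. Nor is it free: under protocol F.18.3 even administrative amendments go to the ethics committees for notification, and investigators sign approved amendments.

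**Conclusion.** The slip is real but clerical, and no change is needed. Rule b carries the wrong name in both documents, and protocol 1c and 2c put a band on the wrong quantity, overlapping intended rule b for P[suc] from 0.05 to about 0.77 at 210 subjects and 0.85 at 240. An analyst working from the SAP would still compute the right quantity and apply it in the right direction, and the literal misreading cannot stop a trial that rule a has not already stopped. The effect on this trial is nil, because enrolment ended for efficacy at the first look and neither futility nor continuation can come into play again.

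The cut-offs assume a normal approximation without borrowing; borrowing shifts them by no more than about 0.02 in the cases examined. That literal rule b never fires without rule a is exact in that approximation and was found by simulation with borrowing. The DSMB charter is not among the documents and may state the rule more fully. The wording could be tidied if the documents were reopened for another reason, but it does not justify an amendment.
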